7.6.4 Subgroup Analysis

Standard descriptive statistics of UACR (both Log-scale and original scale) and change from Baseline to Study Week 12 will be provided for different categories of the following Baseline demographics and lab characteristics subgroups. If data allowed, the primary efficacy endpoint, ie, the change from Baseline to Study Week 12 in log-transformed UACR, with LOCF imputation algorithm will be analyzed using ANCOVA model described in **Section 7.6.1** for each subgroup. The analyses will be based on mITT population.

- Age at study entry (years) (<65; ≥65)
- Sex (male; female)

- Race (African American; not African American)
- eGFR (CKD-EPI) at Baseline (ml/min/1.73m²) (<60; >=60)
- BMI (kg/m²) (below the median; at or above the median)
- SBP (mm Hg) (below the median; at or above the median)
- sUA (mg/dL) (below the median; at or above the median)
- UACR (mg/g) (below the median; at or above the median)
- HbA1C (%) (below the median; at or above the median)Oxidative stress markers (below the median; at or above the median)
 - 8 hydroxy 2' deoxyguanosine (8-OhdG)
 - high sensitivity C reactive protein (hs-CRP)
 - soluble tumor necrosis factor receptor 1 (sTNFR1)

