7.10.1 Determination of Sample Size

Approximately 132 subjects will be randomized at a 1:1:1 ratio to each of the 3 treatment groups (40 mg TMX-049, 200 mg TMX-049, and placebo). Assuming that 10% of all randomized subjects will not be included in the primary endpoint analysis, this would result in approximately 40 subjects per treatment group for inclusion in the primary endpoint assessment.

A sample size of 40 per group will have more than 80% power on the primary endpoint assessment to detect a difference in means of 35% reduction (-0.431 for log-transformed value) of UACR assuming that the common standard deviation (SD) is 0.670 (log-scale) using a 2-group t-test with a 0.050 two-sided significance level.

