2.3 Sample Size and Power

Approximately 132 subjects will be randomized at a 1:1:1 ratio to each of the 3 treatment groups (40 mg TMX-049, 200 mg TMX-049, and Placebo). Assuming that 10% of all randomized subjects will not be included in the primary endpoint analysis, this would result in approximately 40 subjects per treatment group for inclusion in the primary endpoint assessment.

A sample size of 40 per group will have more than 80% power on the primary endpoint assessment to detect a difference in means of 35% reduction (-0.431 for

log-transformed value) of UACR assuming that the common standard deviation (SD) is 0.670 (log-scale) using a 2-group t-test with a 0.050 two-sided significance level.

3. Efficacy and Safety Variables

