7.1 General Principles

All data processing, summarization and analyses will be performed using the Hosted SAS (d-Wise) Environment / Version 9.4 (or later) of the SAS[®] (SAS Institute, Cary, NC) statistical software package.

Unless specified otherwise, data will be displayed using the following treatment group labels, in the order presented:

- Placebo
- TMX-049 40 mg QD
- TMX-049 200 mg QD
- TMX-049 Overall

All data collected will be presented in listings by treatment group, center, subject, and visit (where applicable), unless otherwise specified.

Data will be presented in summary tables by treatment group, assessment, and visit (where applicable).

The category "Missing" will be presented if the number missing is greater than zero for at least 1 treatment group.

Descriptive summary statistics for continuous variables will include the number of observations (N), mean, standard deviation (SD), median, minimum, and maximum. For UACR of original scale, the geometric mean, geometric coefficient of variation (CV), and CV will also be provided.

Descriptive summary statistics for categorical variables will include frequency counts and percentages [n (%)]. Unless stated otherwise in the table shells, the denominator for percentage calculations will be the number of subjects in the pertinent analysis population.

Dates will be displayed as DDMMYYYY.

Analysis and summarization of treatment group comparisons for the primary and secondary efficacy endpoints will be reported in their original measurement units and converted values to accommodate regulatory review by FDA and external authorities, where appropriate.

All significance tests will be 2-sided and use a 0.05 α -level.

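### The subgroup section fits a separate ANCOVA in each level of 12 factors and never estimates a treatment-by-subgroup interaction, so a uniform effect would very likely look like a differential one

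*SAP*

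**What the plan says.** SAP 7.6.4, added by Amendment 1 (April 12, 2019), plans descriptive statistics of UACR by subgroup. Where the data permit, it adds an inferential step in which the primary endpoint "with LOCF imputation algorithm will be analyzed using ANCOVA model described in" Section 7.6.1, once per subgroup, in the mITT population.

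It lists 12 two-level factors. Eight are median splits: BMI, SBP, sUA, UACR, HbA1c, 8-OHdG, hs-CRP and sTNFR1. A typical entry is "UACR (mg/g) (below the median; at or above the median". Four use fixed categories: age, sex, race and eGFR.

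The 7.6.1 model contains treatment and the two randomization strata. It returns a p-value and 95% limits for each dose against placebo. SAP 7.1 adds "All significance tests will be 2-sided and use a 0.05 α -level", with no exemption for subgroups.

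The only treatment interaction in either document is treatment by timepoint, in the repeated-measures model. Neither document adjusts the subgroup tests for multiplicity, labels them exploratory or says how to read them. The statistical section of the protocol (7.10) plans no subgroup analysis, so the SAP is the only place where this is specified.

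**The concern.** The question a subgroup analysis should answer is whether the treatment effect differs between levels of a factor. That is a question about the difference between two effects, which is the interaction. Two separate p-values do not address it. With roughly half the sample in each level, one can fall below 0.05 and the other above it when the two true effects are equal.

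The planned tables would set such pairs of p-values side by side for up to 12 factors and two doses. A reader would then be invited to see responders and non-responders where there may be only sampling variation. In an early proof-of-concept study this matters for the hypotheses carried away from it, not for the primary result.

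**Working it through.** **Inputs.** Effect: "difference in means of 35% reduction (-0.431 for log-transformed value) of UACR" (Protocol 7.10.1). Spread and test: "the common standard deviation (SD) is 0.670 (log-scale) using a 2-group t-test with a 0.050 two-sided significance level" (SAP 2.3). Size: "Approximately 132 subjects will be randomized at a 1:1:1 ratio to each of the 3 treatment groups". Loss: "Assuming that 10% of all randomized subjects will not be included in the primary endpoint analysis".

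**Step 1: reproduce the plan's figure.** ln(0.65) = -0.431. Evaluable per arm = 132 x 0.9 / 3 = 39.6, or about 40. The standard error of a two-arm difference is 0.670 x sqrt(2/40) = 0.150, and 0.431/0.150 = 2.88. Power is 0.820 by the normal approximation and 0.811 by the noncentral t (78 df). This agrees with "A sample size of 40 per group will have more than 80% power on the primary endpoint assessment".

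**Step 2: power within one half of a median split.** With about 20 per arm the standard error is 0.670 x sqrt(2/20) = 0.212, and 0.431/0.212 = 2.03. Power is 0.530 (normal) or 0.509 (t).

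**Step 3: discordance for one factor and one dose under a uniform effect.** With power p in each level, the chance that exactly one is significant is 2p(1-p) = 2 x 0.509 x 0.491 = 0.50. Unequal splits raise it. At 12 versus 28 per arm, powers are 0.326 and 0.657, giving 0.326 x 0.343 + 0.657 x 0.674 = 0.55. At 8 versus 32 the result is 0.62.

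**Step 4: all factors together.** The maximum number of within-level tests is 12 x 2 x 2 = 48. Multiplying independent probabilities would overstate the risk, because every factor splits the same patients. The check was therefore by simulation: 4,000 trials per setting, three arms of 40, normal errors with SD 0.67, and 12 median splits unrelated to outcome. The documents give no correlation between factors, so 0, 0.3 and 0.6 were assumed. With a true effect of -0.431 in everyone on either dose:

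| Assumed correlation | At least one discordant factor, one dose | Same, both doses | Mean discordant factors of 12, per dose | Mean false interactions of 12, per dose |
|---|---|---|---|---|
| 0 | 0.927 | 0.988 | 6.12 | 0.60 |
| 0.3 | 0.924 | 0.985 | 6.04 | 0.60 |
| 0.6 | 0.899 | 0.976 | 6.10 | 0.61 |

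Over both doses that is about 12 of 24 factor-dose pairs discordant, against about 1.2 false interactions.

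**Step 5: what an interaction test can and cannot do.** The standard error of a difference between levels is 0.670 x sqrt(4/20) = 0.300. Power for a between-level difference of 0.431 is Φ(0.431/0.300 - 1.96) = 0.30. It reaches 0.82 only at 0.862.

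Multiplicity remains. Under the uniform effect, the chance of at least one false interaction is 0.36 to 0.46 for one dose and 0.57 to 0.68 over both doses, testing each dose at an unadjusted 0.05. One joint 2-df test per factor lowers it: a separate simulation of 1,000 trials with no drug effect and independent factors gave 0.48, close to 1 - 0.95^12 = 0.46.

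**The case against.** The best case for the plan has four parts.

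First, 7.6.4 leads with descriptive statistics, its ANCOVAs are conditional on the data, and no text compares levels or declares a responder group from a pair of p-values. This is true and limits the seriousness. It does not explain why the model omits the one quantity that measures a difference in effect while producing p-values that cannot.

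Second, part of what is wanted is already planned. The 7.6.1 output includes 95% limits in each subgroup, and SAP 7.6.5.1 plots UACR change against nine of the 12 factors on their continuous scale. Those help a careful reader, but neither is an interaction estimate.

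Third, a reader might infer that these subgroups will choose the next trial's population and that the method will therefore cause false selections. The documents do not support that: the objectives contain no subgroup question, and no selection rule is stated.

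Fourth, a reader might take the false-positive rate with no drug effect as a harm of the missing interaction. Simulated, it is 0.61 to 0.68 for at least one significant level over both doses. Unadjusted per-dose interaction tests give about the same (0.56 to 0.68), so that figure reflects multiplicity and not the absence of an interaction term. The discordance result under a uniform effect does reflect the missing term, and it stands.

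**Conclusion.** The concern holds as an inexpensive improvement to the analysis plan. As written, 7.6.4 cannot show whether the effect differs between levels. If the drug works uniformly at the design effect, at least one spurious contrast between a significant and a non-significant level is near certain: about 0.98 over both doses, and 0.90 to 0.93 for a single dose.

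These figures assume 40 evaluable subjects per arm, normal errors, factors unrelated to outcome, no adjustment for the strata terms, and that every level has enough data to be fitted. The simulation treats all 12 factors as median splits. It would be wrong to read 20 per arm into all of them, because age, sex, race and eGFR have fixed categories whose sizes the documents do not give. Unequal splits make discordance per factor more likely.

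The primary analysis and its conclusion are untouched.

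**What to change.** In SAP 7.6.4, replace the separate fits with one model per factor on the full mITT set, containing treatment, subgroup, treatment-by-subgroup and the 7.6.1 terms. For each factor report:

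- the effect of each dose against placebo in each level, with 95% CI;
- the interaction estimate for each dose, with 95% CI;
- one joint 2-df interaction p-value.

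Omit within-level p-values. State that the section is exploratory and unadjusted for multiplicity.

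The cost is a change of SAP wording and one model per factor in place of two; no new data are needed. The drawback is that most interaction results will be inconclusive, with about 30% power for a between-level difference of 0.431. Across 12 factors a false interaction also remains quite likely: about 0.5 with joint tests, and up to about 0.7 if each dose is tested separately. The exploratory label should say this.

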Subjects who meet all eligibility criteria, including UACR 200 to 3000 mg/g and eGFR ≥ 30 ml/min/1.73m² at both Visit 1 and Visit 2 and who also have $\geq 80\%$ study medication compliance during the 2-week placebo run-in phase, will be randomized at Visit 3 in a 1:1:1 ratio to 1 of 3 treatment groups: Placebo, 40 mg of TMX-049, or 200 mg of TMX-049. Approximately 132 subjects will be randomized, with the expectation that 40 subjects per treatment group will complete 12 weeks of treatment and be included in the primary endpoint assessment. Randomization will be stratified by sUA (< 6.0 versus ≥ 6.0 mg/dL) and UACR (200 to < 300 mg/g versus 300 to ≤ 3000 mg/g) levels obtained at Visit 2. Study medication will be self-administered by the subject qd in the morning at about the same time each day and taken with food (breakfast or a snack), rather than on an empty stomach during the randomized treatment phase beginning on the day after Visit 3 and continued until the morning prior to Visit 6. The time of dosing and time of any food intake will remain consistent during the period of randomized treatment.

Randomized study subjects will return to the site after 2 (Visit 4), 6 (Visit 5), and 12 weeks (Visit 6) of double-blind treatment. Study medication compliance will be assessed by pill count at each visit. First-morning void urine samples will be collected on 2 consecutive days prior to each visit. Urine and blood samples for determination of eGFR, sUA levels, and other laboratory tests will be obtained prior to and after initiation of randomized treatment. Results of sUA and UACR will not be reported to Investigators, subjects, and the Sponsor staff during the randomized treatment phase of the study. The time of PK sample acquisition, the time of dosing prior to the PK sample acquisition, and whether the subject took study medication with or without food will be recorded in the appropriate sections of the case report form (CRF) based on verbal communications with the subjects.

[figure not shown]
At Visit 4, a sample will be obtained prior to TMX-049 dosing (trough sample). At Visit 5, a sample will be obtained 3 ± 1 hours after study medication dosing (t_{\max} sample). The timing of dosing can be adjusted to the time of visiting. At Visit 6, a sample will be obtained ≥ 6 hours (the ideal target is ≥ 8 hours) after study medication dosing (elimination phase sample). If a subject cannot visit within the

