7.6 Efficacy

7.6.1 Primary Efficacy Analysis

The primary efficacy endpoint is the change from Baseline to Study Week 12 (Study Visit 6) in log-transformed UACR. The analysis will be based on the mITT population.

The UACR values from Study Visits 2 to 7 are calculated as the mean result from 2 consecutive day mid-stream, first morning void urine samples that are submitted on the morning before and on the day of study visits. If only 1 sample is available, the measurement from that sample is used.

Baseline UACR is defined as the mean of UACR from urine samples collected on Study Visit 3 (Randomization day).

For the primary analysis of the primary efficacy endpoint, the last-observation-carried-forward (LOCF) imputation algorithm will be used, where the last recorded post-baseline value for the same subject is carried forward to the missing Study Week 12 visit.

The change from Baseline to Study Week 12 in log-transformed UACR will be analyzed in an analysis of covariance (ANCOVA) model with randomized treatment, randomization strata of sUA (<6.0 vs \geq 6.0 mg/dL) and UACR (200 to <300 mg/g vs 300 to \leq 3000 mg/g) levels as independent variables. The least square mean (LS mean), p-value, and the corresponding 95% confidence limit (CL) for the change in log-transformed UACR in each treatment group, and the difference of change in log-transformed UACR between each TMX-049 treatment group versus Placebo group will be presented. The adjusted geometric mean of Week 12 to Baseline ratio in UACR with the corresponding 95% CLs for each treatment group, and the ratio of the adjusted geometric mean of Week 12 to Baseline ratio achieved within each treatment group relative to that achieved with Placebo group with 95% CLs will also be provided.

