7.6.5 Secondary Efficacy Endpoints Analysis

Analysis of the secondary efficacy endpoints will be based on mITT population and PP population. Descriptive statistics for secondary efficacy endpoints will be presented by treatment group and by study visit where appropriate. All post-baseline data collected will be used in the analyses, including observations occurring after discontinuation of study drug.

7.6.5.1 Change in eGFR, UACR, and sUA from Baseline to Study Weeks 2, 6, 12/ET, and Follow-up Visit

For each of these secondary efficacy endpoints, the ANCOVA model using LOCF described for the primary efficacy endpoint in **Section 7.6.1** will be fitted for the change from Baseline to each specific timepoint, ie, Study Week 2, Week 6, Week 12, and Follow-up Visit.

The MMRM and all observed data (excluding data collected at Follow-up visit) described for the primary efficacy endpoint in **Section 7.6.2** will be fitted for each of these endpoints also.

Note: In the above ANCOVA and MMRM models, Baseline eGFR will be included as a covariate to model change in eGFR from Baseline.

For each of these endpoints, 3 figures will be generated by treatment group: figure to present the mean change from Baseline by visit; figure to present the LS mean change from Baseline to Study Week 12 from the ANCOVA model, and figure to present the LS mean change from Baseline to each post-baseline study weeks from the MMRM.

In addition, the following scatter plots will be generated by treatment group:

- Change in UACR at Study Week 12 from Baseline versus Baseline UACR

- Change in UACR at Study Week 12 versus change in eGFR at Study Week 12 from Baseline
- Change in UACR at Study Week 12 from Baseline versus Baseline eGFR
- Change in UACR at Study Week 12 from Baseline versus Baseline sUA
- Change in UACR at Study Week 12 from Baseline versus Change in sUA at Study Week 12
- Change in UACR at Study Week 12 from Baseline versus Baseline BMI
- Change in UACR at Study Week 12 from Baseline versus Baseline SBP
- Change in UACR at Study Week 12 from Baseline versus Baseline HbA1C
- Change in UACR at Study Week 12 from Baseline versus Baseline 8-OHdG
- Change in UACR at Study Week 12 from Baseline versus Baseline hs-CRP
- Change in UACR at Study Week 12 from Baseline versus Baseline sTNFR1
- Change in eGFR at Study Week 12 from Baseline versus Baseline eGFR
- Change in eGFR at Study Week 12 from Baseline versus Baseline sUA

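### The UACR subgroup split and the UACR change plot reuse the Visit 3 value that is subtracted to form the change, so per-arm results by baseline level carry regression to the mean

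*SAP*

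**What the plan says.** - **Baseline.** SAP 7.6.1 states that "Baseline UACR is defined as the mean of UACR from urine samples collected on Study Visit 3". The primary endpoint is log UACR at Week 12 minus log UACR at that Baseline.
- **Subgroups.** SAP 7.6.4 lists Baseline characteristics as subgroup variables, among them "UACR (mg/g) (below the median; at or above the median". Each half gets descriptive change from Baseline and, where the data allow, the 7.6.1 ANCOVA. That model reports an LS mean, p-value and 95% limits for each arm as well as for each dose against placebo.
- **Plot.** SAP 7.6.5.1 asks for a by-arm scatter plot of "Change in UACR at Study Week 12 from Baseline versus Baseline UACR".
- **A second pre-randomisation value.** Visit 2 supplies two first-morning voids. Randomisation is stratified on UACR and sUA "levels obtained at Visit 2" (SAP 2.2).
- **Baseline visit in the protocol.** Protocol 7.1 describes the Visit 2 samples as serving the Baseline UACR determination, and Protocol 7.10.2 exempts UACR from its Visit 3 baseline rule. SAP 7.6.1 uses Visit 3. The two documents do not agree.

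Neither document mentions regression to the mean or limits how the per-arm subgroup results or the plot are to be read.

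**The concern.** The random part of the Visit 3 measurement enters the grouping with a plus sign and the change with a minus sign. Subjects whose Visit 3 value happens to be high tend to land in the upper half and then appear to improve. Those whose value happens to be low appear to worsen. This occurs in every arm, placebo included, without any drug effect, and it gives the scatter plot a downward slope.

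This is a proof-of-concept study with two active arms. A per-arm table showing a significant fall at high UACR in both doses invites the conclusion that high-UACR patients respond, and that conclusion could steer enrichment of a later trial.

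**Working it through.** **The plan's own figure.** Protocol 7.10.1 claims that "A sample size of 40 per group will have more than 80% power on the primary endpoint assessment" for "a difference in means of 35% reduction (-0.431 for log-transformed value) of UACR", with SD 0.670, "using a 2-group t-test with a 0.050 two-sided significance level".
- ln(0.65) = -0.431, and 132 × 0.9 / 3 = 39.6, about 40 per arm.
- 0.431 / (0.670 × √(2/40)) = 2.877, and 2.877 - 1.960 = 0.917. Power is 82.0% by the normal approximation and 81.1% by noncentral t on 78 df. The claim is reproduced.

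**Inputs for the check.**
- SD of change in log UACR, s = 0.670. This reads the sample-size SD as the SD of the primary endpoint.
- SD of Baseline log UACR, b: not in the documents. Assumed 0.8, range 0.6 to 1.1. As a guide, a log-uniform spread over 200 to 3000 mg/g gives ln(15)/√12 = 0.78.
- Equal variance at Visit 3 and Week 12, no drug effect, one pooled median. The SAP does not say whether the median is pooled.

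**Formulas.** For a normal distribution on the log scale:
- slope of change on Baseline = -s²/(2b²)
- correlation of change with Baseline = -s/(2b)
- mean log change in the upper and lower half = -/+ √(2/π) × s²/(2b)

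With s² = 0.4489 and √(2/π) = 0.798:

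| b | slope | mean log change | upper half | lower half |
|---|---|---|---|---|
| 0.6 | -0.623 | -/+0.298 | -25.8% | +34.8% |
| 0.8 | -0.351 | -/+0.224 | -20.1% | +25.1% |
| 1.1 | -0.185 | -/+0.163 | -15.0% | +17.7% |

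At b = 0.8 the correlation is -0.670/1.6 = -0.42, and the shift of 0.224 is 52% of the design effect (0.224/0.431). If s were 0.50 with b = 0.8, the figures would be -11.7% and +13.3%.

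**Simulation with 200 to 3000 mg/g required at Visits 1 and 2.**
- Independent visit errors: -19% to -24% (upper) and +23% to +31% (lower).
- Autocorrelated errors: the upper-half fall is about 16% to 21%.

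**Chance of a spurious per-arm result.** Take 20 subjects per arm in a half and a one-sample test of no change. At b = 0.8 the within-half SD is 0.631, so the noncentrality is 0.224/(0.631/√20) = 1.59 and the test is significant in about 33% of null cases. For b from 0.9 down to 0.7 the rate is 26% to 42%.

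**Planned LS means.** The figures above are raw geometric means. LS means that weight the two Visit 2 UACR strata equally come out near -30% to -34% (upper) and +17% to +25% (lower), because only 2% to 9% of the upper half were below 300 mg/g at Visit 2. The SAP does not state the weighting.

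**Grouping by Visit 2, change still from Visit 3.**
- Independent errors: 0% in both halves, correlation 0.00.
- Autocorrelated errors: a fall of about 5% to 14% remains in the upper half, depending on how the autocorrelation is modelled.

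**Precision of the dose-placebo contrast.** The residual SD in a half is about 0.625 with the Visit 3 split. It is about 0.67 with the Visit 2 split alone (0.67/0.625 = 1.07) and about 0.57 to 0.58 with the Visit 2 split and Baseline log UACR as covariate.

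**The case against.** The strongest defence is that no randomised comparison is harmed. Within either half, the artefact is the same in expectation in all three arms and cancels in dose minus placebo. Tables show placebo first, the plots are by arm, the subgroup ANCOVA is conditional on the data allowing it, and no alpha or decision rule depends on it. All of that stands, and it limits the weight of the point. It does not dispose of it, because the SAP also plans a per-arm LS mean, p-value and confidence limits in each half, with no caution on reading them.

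Several stronger readings are tempting and are not supported:
- A reader might infer that the subgroup dose effects are biased. They are not, by this mechanism.
- A reader might infer that -20% and +25% are facts about this trial. They rest on a baseline SD that the documents do not give.
- A reader might infer that the cause is the missing baseline covariate in the 7.6.1 model, and that adding it alone would cure the per-arm results. It would not: LS means are evaluated at the subgroup's own mean baseline, so the upper-half ratio does not move.
- A reader might carry the figures over to the plot of "Change in eGFR at Study Week 12 from Baseline versus Baseline eGFR". The documents give no variability for eGFR, so no size can be stated, and the eGFR change models already contain Baseline eGFR.

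It is also fair to say that the disagreement on the baseline visit comes first. If it is settled as Visit 2, the roles of the two visits swap.

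**Conclusion.** The point holds for the per-arm UACR subgroup changes, their p-values and confidence limits, and the by-arm plot of UACR change against Baseline UACR. With no drug effect, raw per-arm geometric means are expected to change by about -15% to -26% in the high half and +18% to +35% in the low half. This rests on 0.670 being the SD of log change, equal variance at Visit 3 and Week 12, and an assumed baseline log SD of 0.6 to 1.1. Autocorrelated within-subject variation makes the effect smaller, and the planned LS means may differ from these raw means. In an active arm the artefact adds to any drug effect. It does not touch the primary result or the dose-placebo contrasts, so this is an improvement the SAP should make, not a threat to the trial's main conclusion.

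**What to change.** 1. In SAP 7.6.4, form the UACR subgroup from the Visit 2 UACR, split at the Visit 2 median. Keep Visit 3 as Baseline for the change.
2. Within these subgroups, fit the 7.6.3 model, with Baseline log UACR as covariate. Its purpose is precision: the Visit 2 split alone would raise the residual SD of the dose-placebo contrast by about 7%, and the covariate more than recovers that.
3. If the randomisation stratum (below 300 against 300 mg/g and above) is used as the subgroup, drop it as a model factor, since it is then constant. The same happens in the upper half of a Visit 2 median split whenever that median is 300 mg/g or more.
4. In SAP 7.6.5.1, plot UACR change against Visit 2 UACR.
5. Settle the baseline visit between Protocol 7.1 and 7.10.2 and SAP 7.6.1. If it becomes Visit 2, group and plot by Visit 3 instead.
6. State that this reduces the artefact but may not fully remove it, and that subgroup results are to be read as differences from placebo.

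The cost is SAP wording and one derived variable, with no new data. The downside is that the grouping value is about 2 weeks older than Baseline.
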